## ABBREVIATIONS

ACE-I	Angiotensin-converting-enzyme inhibitor
ARB	Angiotensin II receptor blocker
ADR	Adverse drug reaction
AE	Adverse event
DSMB	Data safety monitoring board
eCRF	Electronic case report forms
GFR	Glomerular filtration rate
ICU	Intensive care unit
IV	Intravenous
LAR	Legally authorized representative
LFT	Liver function test
MIC	Minimum inhibitory concentration
NSAIDs	Nonsteroidal anti-inflammatory drug
PI	Principal investigator (a clinician responsible for one site)
RCT	Randomized control trial
SAE	Serious adverse events
S/F	SpO 2 /FiO 2 ratio
SOC	Standard of Care
SOFA	Sequential Organ Failure Assessment
SOP	Standard operating Procedure

## 1.0 Protocol Synopsis

### Study Design

Blinded, single-center, placebo-controlled randomized clinical trial

### Study Aim

To compare the effect of oral magnesium citrate plus a the probiotic Floranex versus placebo on clinical outcomes, determined by the oxygen area under the curve, among adults with COVID-19 requiring hospitalization.

### Primary Outcome

1. Change in COVID Ordinal Outcome Scale (Appendix E) through Day 7 after completion of therapy

### Secondary Outcomes

1. Time to recovery, which is the time to the earlier of final liberation from supplemental oxygen or hospital discharge
2. Hospital mortality to 28-day mortality (assessed on Study Day 29 from randomization)
3. Time to discharge to 28 days after treatment
4. Quantitative change in nasal viral titer
5. Change in systemic CD4+ and CD8+ T cell cytokine expression
6. Change in Oxygen AUC of SaO2/FiO2 through Day 7
7. Quantitative change in systemic immune profile
8. Oxygen-free days through Day 28
9. Ventilator-free days through Day 28
10. Vasopressor-free days through Day 28
11. ICU-free days through Day 28
12. Hospital-free days through Day 28

### Inclusion Criteria

1. Age  $\geq$ 18 years
2. Currently hospitalized or in an emergency department with anticipated hospitalization.
3. Symptoms of acute respiratory infection, defined as one or more of the following:
  - a. Cough
  - b. Fever ( $> 37.5^{\circ}$  C /  $99.5^{\circ}$  F)
  - c. Shortness of breath (operationalized as any of the following: subjective shortness of breath reported by patient or surrogate; tachypnea with respiratory rate  $\geq 22$  /minute; hypoxemia, defined as SpO2  $< 92\%$  on room air, new receipt of supplemental oxygen to maintain SpO2  $\geq 92\%$ , or increased supplemental oxygen to maintain SpO2  $\geq 92\%$  for a patient on chronic oxygen therapy).
  - d. Sore throat
  - e. Anosmia
4. Laboratory-confirmed SARS-CoV-2 infection within 10 days prior to randomization
5. Ability to manage own stool care

### Exclusion Criteria

1. Pregnancy
2. Breast feeding

3. Mechanical ventilation
4. Current infectious or noninfectious diarrheal illness
5. Unable to randomize within 21 days after onset of acute respiratory infection symptoms
6. Unable to randomize after hospital arrival
7. Colonic obstruction
8. Unresolved hypovolemia
9. Hypermagnesemia
10. Diagnosis of long QT syndrome
11. Known allergy to magnesium citrate the probiotic Floranex
12. Unresolved electrolyte imbalance, such as hypokalemia or hypocalcemia.
13. Receipt of >1 dose of magnesium citrate, the probiotic Floranex or any other colonic cleansing agent within 7 days prior to enrollment
14. Inability to receive enteral medications
15. Refusal or inability to be contacted on Day 7 for clinical outcome assessment if discharged prior to Day 7
16. Concurrent medical illness that interferes with clinical assessments
17. The treating clinical team does not believe equipoise exists regarding the use of magnesium citrate plus a the probiotic Floranex for the treatment of this patient
18. Immunologically vulnerable patients, such as AIDS patients or neutropenic patients
19. Participating in any other COVID-19 therapeutic trials.

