#### **Exclusion Criteria**

- 1. Prisoner
- 2. Pregnancy
- 3. Breast feeding
- 4. Current infectious or noninfectious diarrheal illness
- 5. Unable to randomize within 21 days after onset of acute respiratory infection symptoms
- 6. Unable to randomize after hospital arrival
- 7. Colonic obstruction
- 8. Unresolved hypovolemia
- 9.  $\text{CrCl} < 30\text{ml/min}$
- 10. Hypermagnesemia
- 11. Diagnosis of Long QT syndrome
- 12. Known allergy to magnesium citrate or the probiotic Floranex
- 13. Unresolved electrolyte imbalance such as hypokalemia or hypocalcemia. The patient can be enrolled if electrolytes are corrected and sustained.
- 14. Receipt of  $> 1$  dose of magnesium citrate or any other colonic cleanser in the 7 days prior to enrollment
- 15. Inability to receive enteral medications
- 16. Refusal or inability to be contacted on Day 15 for clinical outcome assessment if discharged prior to Day 15
- 17. Concurrent medical illness that interferes with clinical assessmentPrevious enrollment in this trial
- 18. The treating clinical team does not believe equipoise exists regarding the use of magnesium citrate plus the probiotic Floranex for the treatment of this patient.
- 19. Participating in any other COVID-19 therapeutic trial

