#### **3.3 Justification of Exclusion Criteria**

The exclusion criteria are primarily designed for patient safety. In addition to excluding specific vulnerable populations (e.g., prisoners), these criteria are designed to exclude patients for whom receipt of magnesium citrate plus a the probiotic Floranex might increase the risk of serious adverse events.

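### The synopsis and Section 3 eligibility lists differ on nine items and nothing says which governs; ventilation, immune status, renal function and contact day matter most

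*Combined protocol and SAP*

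**What the plan says.** The Section 1.0 synopsis has its own inclusion and exclusion lists. Section 3 (3.1 and the exclusion list that follows it) states them again.

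The synopsis alone excludes mechanical ventilation and "Immunologically vulnerable patients, such as AIDS patients or neutropenic patients". It alone requires "Ability to manage own stool care" and accepts anosmia as a qualifying symptom. Section 3 alone excludes prisoners, creatinine clearance below 30 ml/min, and previous enrolment (the last is run on to the end of item 17).

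Two shared criteria are worded differently. On prior exposure, the synopsis has "Receipt of >1 dose of magnesium citrate, the probiotic Floranex or any other colonic cleansing agent within 7 days prior to enrollment", while Section 3 refers to more than one "dose of magnesium citrate or any other colonic cleanser in the 7 days prior to enrollment" and does not name Floranex. On follow-up contact, the synopsis has "Refusal or inability to be contacted on Day 7 for clinical outcome assessment if discharged prior to Day 7" and Section 3 has "Refusal or inability to be contacted on Day 15 for clinical outcome assessment if discharged prior to Day 15".

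Section 3 also adds to the shared electrolyte exclusion: "The patient can be enrolled if electrolytes are corrected and sustained". Both lists already limit that exclusion to unresolved imbalance, so I read the sentence as an explanation and do not count it.

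Section 3.5 has one electronic form determine eligibility, and Section 3.7 requires eligibility to be confirmed before randomization. Neither says which list the form must carry.

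**The concern.** Eligibility defines the trial population, and here it depends on which page the screener reads. Taken at face value, an otherwise qualifying patient who is ventilated or neutropenic is out under the synopsis and in under Section 3. A patient with creatinine clearance below 30 ml/min is out under Section 3 and in under the synopsis, which conflicts with the protocol's own safety text.

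The contact criterion has a more directly statistical consequence. It exists to secure the outcome assessment in patients discharged early. Section 3's version still covers everyone discharged before Day 7, but it asks about the wrong day. A patient who can be reached on Day 15 but not during Days 7 to 14 would pass it, and the Day 7 score could be missing. Section 7 states no missing-data rule, and with 30 patients each such loss is 1/30 = 3.3% of the sample.

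**Working it through.** The check is a comparison of the two lists item by item, followed by a search of the rest of the protocol for text bearing on each difference.

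| Item | Synopsis | Section 3 | Other text |
|---|---|---|---|
| Mechanical ventilation | excluded | absent | mixed |
| Immunologically vulnerable | excluded | absent | none |
| Own stool care | required | absent | none |
| Anosmia as a symptom | accepted | absent | none |
| Prior Floranex | counts | not named | none |
| Prisoner | absent | excluded | 3.3 agrees with Section 3 |
| Creatinine clearance below 30 ml/min | absent | excluded | 9.1 and 11 agree with Section 3 |
| Previous enrolment | absent | excluded | none |
| Contact day | Day 7 | Day 15 | 4.1, 6.3.1 and 7.1 point to Day 7 |

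**Count.** 4 in the synopsis only + 3 in Section 3 only + 1 difference of scope (Floranex) + 1 with two values (contact day) = 9. Other text bears clearly on 3, leaving 9 - 3 = 6 unsettled. Counting the electrolyte sentence would make the total 10.

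**Neither list works alone.** If the synopsis governs, the renal exclusion that Sections 9.1 and 11 rely on disappears, as does the prisoner exclusion that Section 3.3 cites ("In addition to excluding specific vulnerable populations (e.g., prisoners"). If Section 3 governs, the ventilation and immune exclusions disappear and the Day 15 contact stays.

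**Ventilation.** Section 2.1.4 speaks of non-ICU subjects and leaves more severe disease to later trials. Against that, Section 6.1 allows for an ICU location at enrolment, Section 7.1 reports patients randomized in the ICU separately, and Section 10.1 screens ICUs. Section 10.2 argues for generalizability to severe illness, and Section 10.6 expects many candidates to lack capacity because of critical illness. None of these states a ventilation rule. On the Appendix E scale, hospitalized patients who are not ventilated score 4, 5 or 6 (3 levels), and scores 7, 8 and 9 are the ventilated states (3 more, 6 in all). Without the exclusion, baseline scores of 7 to 9 are not expressly ruled out.

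**Contact day.** Section 6.3.1 sets call windows of Days 7-14 and Days 29-36. Day 15 falls in neither: 15 - 14 = 1 day after the first closes, and 29 - 15 = 14 days before the second opens. Sections 4.1 and 7.1 place the primary outcome at Day 7. Section 4.1's general follow-up through Day 29 and the telephone footnote in Appendix A name no Day 15 contact. The only other Day 15 in the protocol belongs to the external vitamin D trial used for planning in Section 7.1.

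**The case against.** The best defence is that Section 3 is the operative text and the synopsis is a summary. The passages that discuss exclusions (3.3, 9.1 and 11) all match Section 3, while those supporting Day 7 concern outcome timing rather than eligibility. This has force, but no sentence ranks the lists, and giving Section 3 priority would keep the contact day that fits nothing else. Nor is the synopsis merely shorter: it carries exclusions that Section 3 lacks.

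A second defence is that staff could apply both lists together. That would work mechanically, but the protocol does not say to do it, and it would require a Day 15 contact for which no assessment is scheduled.

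Third, several items are small. Anosmia matters only for a patient with no other listed symptom, and previous enrolment is a run-on fragment. That is right, and the weight of the point does not rest on them.

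A reader might also infer more than the documents support:

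- *That the ventilation line alone decides whether baseline scores span 4-6 or 4-9.* This is too strong. ICU enrolment is not ventilated enrolment, since a patient on high-flow oxygen scores 6. Section 2.1.3 places the treatment window before severe respiratory failure, and Section 4.2 has the products taken by mouth. Oral dosing does not close the question, however, because both lists exclude only inability to take enteral medication.
- *That the synopsis-only items are shown to be safety criteria.* Section 3.3 gives a safety purpose for the Section 3 list, not for those items. Section 9.1.2 lists only gas, bloating and diarrhoea as probiotic risks, and nothing ties stool care or immune status to a stated hazard.
- *That renal function is an open question.* Section 9.1 says such patients are excluded. The fault is that the synopsis contradicts this.

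**Conclusion.** The point holds: there are nine differences, no governing list, and four items that matter most. Ventilation and immune status are unresolved anywhere in the protocol. On renal function, the synopsis contradicts the protocol's own safety text. On contact day, Section 3 conflicts with the outcome schedule. Of the five lesser items, Section 3.3 settles prisoners; stool care, prior Floranex, anosmia and previous enrolment remain open.

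The consequence is for who may be enrolled, for safety screening and for the population to which the result applies. A reader might infer a biased treatment comparison, but the documents do not support that: allocation is randomized and blinded, and the Section 7.1 model adjusts for the baseline ordinal score. Nor do they support a claim that patients were wrongly screened, because the eligibility form is not among the documents. They give no basis for estimating how many patients would be affected.

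The conclusion assumes that the electrolyte sentence only explains the shared criterion. It also takes the primary assessment day as Study Day 7, as Sections 4.1 and 7.1 state. The outcome definition in Section 5.1 is worded relative to completion of therapy. If the last treatment day is Day 6, the final adherence day in Appendix A, that wording gives 6 + 7 = Day 13, which is still not Day 15. Ranking four items above the other five is a judgment.

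**What to change.** The sponsor and investigator should reconcile the nine items into one numbered list and use it word for word in the synopsis, Section 3 and the eligibility form. In doing so:

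- Reconcile the synopsis with Section 3, Section 9.1 and Section 11 on renal function.
- Reconcile the ventilation item with Sections 2.1.4, 6.1, 7.1, 10.1, 10.2 and 10.6.
- State whether immune status is a criterion, and treat the lesser items the same way.
- Align the contact-day criterion with the Day 7 primary-outcome assessment and its call window in Section 6.3.1.
- State whether the electrolyte sentence belongs in both lists.

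Which clinical criteria to keep is for the sponsor and investigator; none is proposed here. The cost is a wording amendment and a check of the eligibility form. Sample size and analysis model do not change.

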### **Randomization**

Eligible participants will be randomized 1:1 to magnesium citrate plus the probiotic Floranex versus placebo. Placebo will be carbonated lemon water for magnesium citrate and over-encapsulated microcrystalline pills for Floranex. Randomization will be completed in permuted blocks of variable size.

## 2. TRIAL DESCRIPTION

### 2.1 Background

Coronavirus Disease 2019 (COVID-19) is an acute respiratory infectious illness caused by *severe acute respiratory syndrome coronavirus 2* (SARS-CoV-2). Although the epidemiology has not been fully elucidated, most adults with COVID-19 appear to experience fever, cough, and fatigue and then recover within 1-3 weeks. However, a portion of adults with COVID-19 develop severe illness, typically manifesting as pneumonia and hypoxic respiratory failure, with continued progression to acute respiratory distress syndrome (ARDS) and death in some cases. The incidence and mortality of COVID-19 cases continues to climb in the United States, as well as around the world. While progress for vaccination and identifying therapeutics against SARS-CoV-2 have emerged, the limitations continue to emerge. For example, convalescent plasma was recently demonstrated to hold little promise against COVID-19 severe pneumonia[1]. While remdesivir demonstrates efficacy in hospitalized COVID-19 patients with pneumonia[2], the NIH no longer recommends remdesivir with dexamethasone as an option for hospitalized COVID-19 patients who require mechanical ventilation or ECMO, recommending only dexamethasone instead (COVID-19 Treatment Guidelines Panel. Coronavirus Disease 2019 (COVID-19) Treatment Guidelines. National Institutes of Health. Available at <https://www.covid19treatmentguidelines.nih.gov/>. Accessed 12/07/2020). Thus, data on the safety and effectiveness of magnesium citrate plus the probiotic Floranex for the treatment of COVID-19 are urgently needed to inform clinical practice. In this trial, we will evaluate the safety and effectiveness of magnesium citrate plus the probiotic Floranex for the treatment of adults hospitalized with COVID-19.

#### 2.1.1 COVID-19 Infection

COVID-19 was first identified as a cluster of cases of pneumonia among a group of workers from a seafood wholesale market in Wuhan, China in December 2019. This observation, along with subsequent viral genotyping showing significant genetic similarities to the bat coronaviruses suggest a zoonotic origin, although the specific reservoir and intermediary species remain unclear. The COVID-19 infection represents the seventh coronavirus known to cause disease in humans. Four of the coronaviruses viruses are known to cause symptoms of the common cold in immunocompetent individuals while two others (SARS-CoV and MERS-CoV) have caused recent outbreaks of severe and sometimes fatal respiratory diseases. SARS-CoV-2 appears to exploit the same cellular receptor as SARS-CoV and MERS-CoV, and its severity may similarly result from a predilection for intrapulmonary epithelial cells over cells of the upper airways. Since the first documented human case, COVID-19 has spread exponentially within the United States with 14,823,129 confirmed cases and 282,785 deaths as of December 8, 2020. While most patients recover after a mild, brief illness with fever and cough, the disease has a clinical spectrum ranging from asymptomatic infection to ARDS and death. The most common reasons for ICU care are respiratory failure and ARDS, with a minority developing shock and possibly cardiomyopathy. The case fatality rate is estimated to be 0.25% to 3.0%.

#### 2.1.2 Magnesium citrates as a Therapeutic for COVID-19

Recent recommendations, such as the cessation of remdesivir in intubated COVID-19 patients with severe pneumonia, illustrates an important clinical observation: much of COVID-19 mortality occurs after the virus has been cleared. Viral clearance typically occurs 9-20 days after symptom onset[3]. A similar monkey model of SARS-CoV infection in the African Green Monkey demonstrated clearance of virus from nasal turbinates, nasopharynx, tracheal, proximal and distal lungs within 5-10 days after infection[4]. Similarly, investigators reported that viral loads in SARS-CoV-2-challenged rhesus macaques remain elevated for 10-28 days following primary challenge[5].

A common clinical factor found in persons at risk for COVID-19 severity, such as aging, obesity, diabetes and hypertension, is gut dysbiosis and resulting low grade inflammation with loss of epithelial barrier function[6, 7]. A recent study noted that compared with healthy controls, COVID-19 patients had significantly reduced bacterial diversity, a significantly higher relative abundance of opportunistic pathogens, such as *Streptococcus*, *Rothia*, *Veillonella* and *Actinomyces*, and a lower relative abundance of beneficial symbionts[8, 9]. Another investigation

of faecal samples with signature of high SARS-CoV-2 infectivity had higher abundances of bacterial species, such as *Collinsella aerofaciens*, *Collinsella tanakaei*, *Streptococcus infantis*, *Morganella morganii*, and higher functional capacity for nucleotide de novo biosynthesis, amino acid biosynthesis and glycolysis, whereas faecal samples with signature of low-to-none SARS-CoV-2 infectivity had higher abundances of short-chain fatty acid producing bacteria, *Parabacteroides merdae*, *Bacteroides stercoris*, *Alistipes onderdonkii* and *Lachnospiraceae* bacterium in the stool of COVID-19 patients[10]. These observations support assessing for host metagenomic contributors to COVID-19 morbidity and mortality.

Alterations of the microbiota that lead to intestinal dysbiosis (a microbial imbalance within the intestinal tract) are characterized by a loss or significant decrease in the amount of beneficial bacterial species and/or an outgrowth or population shift of pathogenic species. A growing body of literature implicates the role of the gut microbiome in the severity of chronic viral infections. Perturbation of the gut microbiota during influenza A virus (IAV) infection might favor respiratory bacterial superinfection[11]. Alterations in the gut microbiome itself may affect influenza severity. In general, mice treated with broad spectrum antibiotics display diminished innate and adaptive immune responses, characterized by reduced expression of antiviral genes in alveolar macrophages, more severe bronchiole epithelial degeneration, and higher viral loads compared to untreated mice[12]. Laboratory mice reconstituted with natural microbiota exhibited reduced inflammation and increased survival following influenza virus infection and improved resistance against mutagen/inflammation-induced colorectal tumorigenesis[13]. It has been suggested that gut microbiota can fine-tune the threshold of antiviral immune responses[14], possibly through metabolites such as short chain fatty acids (SCFAs). The critical role of SCFAs in the gut-lung axis is well-recognized, and studies in a mouse model have shown that consumption of SCFAs reduces inflammatory symptoms, and also decreases allergic diseases in the airway through suppression by regulatory T (Treg) cells[15]. Indeed independent reports suggest that alteration of the gut microbiome may positively affect COVID-19 severity. Suggestions, such as the probiotic Floranex and high fiber diets, have been postulated to reduce COVID-19 severity[16]; however, that ability of such interventions to rapidly affect alter the gut microbiome in hospitalized patients, and thus potentially reduce COVID-19 severity, are limited.

Recent investigations of chemical induction of acute lung inflammation demonstrates significant reductions in lung injury among mice housed in germ-free environments ([name], manuscript in preparation). Also, administration of colonic cleansing via magnesium citrate in three hypoxic, COVID-19 patients with pneumonitis resulted in significant clinical improvement within 24-72 hours ([name], manuscript in preparation).

### **2.1.3 Rationale for a Randomized Trial among Hospitalized Patients**

The initial symptoms of COVID-19 develop approximately 2-10 days after infection with the SARS-CoV-2 virus, with the progression to respiratory failure and ARDS occurring approximately 7-10 days after the onset of symptoms. While most adults with COVID-19 recover without complications, patients who require hospitalization experience high rates of complications. In case series of hospitalized patients with COVID-19, up to 26% require ICU admission and up to 17% die in the hospital. The period between onset of symptoms and development of severe respiratory failure represents a potential window for treatment of hospitalized patients to prevent disease progression.

Given the unprecedented public health crisis caused by COVID-19, there is significant interest in finding effective therapies and, specifically, in repurposing approved medications with widespread availability and known safety profiles.

Data on the safety and efficacy of magnesium citrate from randomized trials is urgently needed. A randomized clinical trial demonstrating that magnesium citrate prevents disease progression in hospitalized patients with COVID-19 would provide evidence-based therapy for an ongoing pandemic, as well as important public health impact.

Given the need for effective treatments of COVID-19 and the unclear efficacy and safety of magnesium citrate as a treatment of COVID-19 a randomized clinical trial is urgently needed.

